5.7 Advice to Investigators Related to Potential Drug Interactions

In vitro metabolism studies and studies in mice suggest that DM4 is predominantly metabolized by thiol *S*-methyltransferase to form another highly active metabolite DM4-Me, which is further metabolized into the less active sulfoxide-methyl-DM4 and eliminated in the bile. Because DM4-Me has been shown to be primarily metabolized by CYP3A4 in human hepatic microsomes, its exposure could potentially be increased in the presence of strong CYP3A inhibitors. If concomitant medication with a CYP3A inhibitor cannot be avoided, monitor for risk of increased toxicity. Drinking greater than 1 serving (250 mL) of grapefruit juice per day should be avoided. [Appendix G](#) provides examples of CYP3A inhibitors. An in vitro study evaluating the potential for CYP inhibition demonstrated that DM4 and DM4 Me are not direct inhibitors of the 7 CYP isoforms evaluated, however DM4 showed time-dependent inhibition of CYP3A4 and DM4-Me showed weak time-dependent inhibition of CYP2C8 and CYP2C9. Treatment of subjects with concomitant medications that are sensitive substrates of CYP3A or are CYP3A substrates with a narrow therapeutic index should be avoided (see [Appendix H](#) for examples).

6 EFFICACY ASSESSMENTS

The primary criteria for defining evidence of anticancer activity and also for management of subject care will be a clinical response as defined by RECIST (Version 1.1). Management of subjects in Parts D1, D2, E1, and E2 may also take into consideration tumor response assessed by irRECIST. Efficacy in this study will be explored in subjects on the basis of:

- ORR by the RECIST (Version 1.1);
- TTR;
- DOR;
- PFS; and
- OS.

Efficacy in subjects treated with the combination CX-2009 plus CX-072 (Parts D1, D2, E1, and E2) will be explored additionally on the basis of:

- ORR by irRECIST as defined in the Core ([Appendix A](#))

Please refer to the Core for a description of the efficacy assessments.

7 PHARMACOKINETIC, IMMUNOGENICITY, AND EXPLORATORY BIOMARKER ASSESSMENTS

7.1 Pharmacokinetic Assessments

Concentration versus time data will be tabulated and plotted for the individual and mean CX-2009 (total and intact), CX-2009-conjugated DM4 and free DM4, and DM4-Me analytes and for total and intact CX-072 moieties. PK parameters, including AUC, C_{max} , C_{min} , clearance, and volume of distribution at steady state, will be calculated for CX-2009 (total and intact), DM4 (conjugated and free), and DM4-Me analytes as appropriate and as data allow. Additional parameters such as terminal elimination half-life and accumulation may be calculated, and dose proportionality will be assessed for subjects with sufficient data. Estimates for these parameters will be tabulated and summarized (eg, mean, standard deviation, and coefficient of variation). CX-072 (total and intact moieties) C_{max} and C_{min} will be tabulated individually and summarized using descriptive statistics (eg, mean, standard deviation, and coefficient of variation).

Additional exploratory model-based PK analyses may be conducted and the results of these analyses may be reported in a document separate from the clinical study report.

Plasma samples will be drawn from a site other than the infusion site (ie, contralateral arm) on days of infusion at the times indicated in [Appendix B](#).

If the infusion was interrupted, the reason for interruption will also be documented in the eCRF and a sample will be collected at the end of the infusion and at the times specified after the end of infusion.

7.2 Exploratory Biomarkers

Probody therapeutics differ from unmodified mAbs by the recombinant addition of a prodomain at the amino-terminus of the light chain, which blocks the antibody binding to its target antigen and can be removed by tumor-associated protease activity. In this way, CX-2009 and CX-072 are expected to be activated in tumors and bind to their targets, CD166 and PD-L1 respectively, but to be relatively inactive outside of the TME.

The overall goal of the biomarker portion of CTMX-M-2009-001 is to explore A) Probody therapeutic mechanistic proof of concept, and B) potential predictive markers associated with the clinical activity of CX-2009 alone or in combination with CX-072.

This information will help to further build the translational program for the development of CX-2009 and CX-072.

The presence of activated proteases capable of activating the Probody therapeutics in the human TME will be assessed using a semi-quantitative zymographic assay that combines ex vivo incubation of the Probody therapeutic probe in sections of biopsy and capillary electrophoresis analysis to measure the intact and cleaved Probody therapeutics. A similar capillary

electrophoretic method will be used to measure the Probody therapeutic activation in plasma and on-treatment tumor biopsies following administration of CX-2009 alone or in combination with CX-072. The expression of the target, CD166, will be evaluated using a Clinical Laboratory Improvement Amendments of 1998-validated IHC assay.

Exploratory studies will include the evaluation of:

- Probody therapeutic activation in tumors and in blood;
- The potential link between tumor markers, such as the target of CX-2009 (ie, CD166), the target of CX-072 (ie, PD-L1) and the biological activity of CX-2009 alone or in combination with CX-072;
- The potential link between exploratory biomarkers in blood and the biological activity of CX-2009 alone or in combination with CX-072; and
- The presence of activated proteases in the human TME capable of removing the peptide mask and thereby activating the Probody therapeutic.

7.3 Exploratory Biomarkers Collection

In order to address the above objectives, tissue samples will be collected throughout the course of the study.

For Parts A and C1, pretreatment and on-treatment tumor biopsies will be optional. For the subjects who consent, tumor biopsies will be collected during the Screening Period (baseline) and 3 to 5 days after the first dose of CX-2009, provided that the tumor is accessible and a biopsy is deemed safe by the treating physician.

For Part A2, tumor biopsies (fixed and frozen) are required 3 to 5 days after the first dose of CX-2009, provided that the tumor is accessible and a biopsy is deemed safe by the treating physician.

For Parts B and C2, consent to pretreatment and on-treatment tumor biopsies will be mandatory in at least 7 subjects for each tumor type. For these subjects, tumor biopsies (fixed and frozen) will be collected during the Screening Period (baseline) and 3 to 5 days after the first dose of CX-2009, provided that the tumor is accessible and a biopsy is deemed safe by the treating physician.

For Parts D1, D2, E1, and E2, on-treatment tumor biopsies will be optional. For the subjects who consent, tumor biopsies will be collected 3 to 5 days after the third dose, provided that the tumor is accessible and a biopsy is deemed safe by the treating physician.

8 SAFETY ASSESSMENTS

8.1 Adverse Events

An AE is defined as any untoward medical occurrence in a clinical investigation subject administered a pharmaceutical product, which does not necessarily have a causal relationship with this treatment. An AE can therefore be any unfavorable and/or unintended sign (including an abnormal laboratory finding), symptom, or disease temporally associated with the use of an investigational medicinal product, whether or not related to the investigational medicinal product. All AEs, including observed or volunteered problems, complaints, or symptoms, are to be recorded on the appropriate eCRF.

Progressive disease in and of itself is not considered an AE or SAE. Progressive disease is an efficacy finding and should not be reported unless the progressive disease results in death during the reporting period (from date of signed informed consent to 30 days post last study treatment administration). On-study deaths, reported as SAEs due to progressive disease and considered unrelated to study drug will be excluded from treatment-emergent AE analysis.

8.1.1 Suspected Adverse Reaction

A suspected adverse reaction is an AE for which there is a reasonable possibility that the study drug(s) caused the AE. For the purposes of Investigational New Drug safety reporting, “reasonable possibility” means there is evidence to suggest a causal relationship between the study drug(s) and the AE. Suspected adverse reaction implies a lesser degree of certainty about causality than adverse reaction, which means any AE caused by the study drug(s).

8.1.2 Life-Threatening Adverse Event or Life-Threatening Suspected Adverse Reaction

An AE or suspected adverse reaction is considered “life threatening” if, in the view of either the Investigator or Sponsor, its occurrence places the subject at immediate risk of death. It does not include an AE or suspected adverse reaction that, had it occurred in a more severe form, might have caused death.

8.1.3 Serious Adverse Event or Serious Suspected Adverse Reaction

An AE or suspected adverse reaction is considered “serious” if, in the view of either the Investigator or Sponsor, it results in any of the following outcomes:

- Death
- A life-threatening AE (see definition above)
- Inpatient hospitalization or prolongation of existing hospitalization
- A persistent or significant incapacity or substantial disruption of the ability to conduct normal life functions

- A congenital anomaly/birth defect
- Important medical events: Based on medical judgment, may jeopardize the subject or may require medical or surgical intervention to prevent one of the outcomes listed above (eg, anaphylaxis, allergic bronchospasm requiring intensive treatment in an emergency room or at home, blood dyscrasias or convulsions that do not result in inpatient hospitalization).

8.1.4 Unexpected Adverse Event or Unexpected Suspected Adverse Reaction

An AE or suspected adverse reaction is considered “unexpected:”

- If it is not listed in the IB or is not listed at the specificity or severity that has been observed; or
- If an IB is not required or available, is not consistent with the risk information described in the general investigational plan or elsewhere in the current application, as amended.

For example, under this definition, hepatic necrosis would be unexpected (by virtue of greater severity) if the IB referred only to elevated hepatic enzymes or hepatitis. Similarly, cerebral thromboembolism and cerebral vasculitis would be unexpected (by virtue of greater specificity) if the IB listed only cerebral vascular accidents.

“Unexpected,” as used in this definition, also refers to AEs or suspected adverse reactions that are mentioned in the IB as occurring with a class of drugs or as anticipated from the pharmacological properties of the drug, but are not specifically mentioned as occurring with the particular drug under investigation.

8.2 Adverse Event Classification

8.2.1 Relationship to Investigational Drug

The Investigator’s assessment of causality must be provided for all AEs (serious and non-serious). An Investigator’s causality assessment is the determination of whether there exists a reasonable possibility that the study drug caused or contributed to an AE. The relationship to study drug will be categorized as “Yes” or “No.”

8.2.2 Severity

The severity of an event describes the degree of impact upon the subject and/or the need for, and extent of, medical care necessary to treat the event.

AE grading will be defined by the NCI CTCAE v4.03. In the event that the NCI CTCAE v4.03 does not apply, the severity descriptions in [Table 11](#) will be used to describe the maximum intensity of the AE.

Table 11. Adverse Event Severity

Grade	Description
Grade 1	Mild; asymptomatic or mild symptoms; clinical or diagnostic observations only; intervention not indicated
Grade 2	Moderate; minimal, local or noninvasive intervention indicated; limiting age-appropriate instrumental activities of daily living.
Grade 3	Severe or medically significant but not immediately life-threatening; hospitalization or prolongation of hospitalization indicated; disabling; limiting self-care activities of daily living
Grade 4	Life-threatening consequences; urgent intervention required
Grade 5	Death related to an adverse event

Source: https://www.eortc.be/services/doc/ctc/CTCAE_4.03_2010-06-14_QuickReference_5x7.pdf. Accessed 19 November 2019.

8.3 Exposure in Utero

The subject will be instructed to notify the Investigator if the subject or subject's partner becomes pregnant during the study. The Investigator must notify the Sponsor or designee within 24 hours via the Pregnancy Notification Form to meet the 24-hour reporting requirement. If it is not possible to report the pregnancy via the Pregnancy Notification Form, telephone or e-mail will be acceptable. The Investigator should obtain informed consent/assent from the subject or subject's partner allowing the Investigator to obtain information regarding the pregnancy and its outcome. If the subject or subject's partner provides informed consent/assent, the Investigator should follow the pregnancy until outcome. A final Pregnancy Notification Form should be completed when the outcome of the pregnancy is known.

Although not an AE per se, pregnancy in either a patient or the partner of a patient taking trial medication should be reported as an SAE to facilitate outcome monitoring by the Sponsor.

Abortion, whether therapeutic or spontaneous, should always be classified as an SAE (as the Sponsor considers these to be medically significant), recorded on the eCRF, and expeditiously reported to the Sponsor as an SAE.

8.4 Monitoring of Adverse Event Data

Safety information in the study will be monitored on an ongoing basis by the Medical Monitor and Investigators and discussed at regular teleconferences.

AEs occurring during the reporting period (up to and including 30 days after administration of the last dose of study drug for all AEs and up to and including 90 days after administration of the last dose of study drug for all irAEs related to CX-072) should be followed until resolution to baseline status, initiation of a new therapy, or stabilization.

Proper instruction will be provided to each site to ensure prompt reporting and communication between the Sponsor, Investigators, Food and Drug Administration (FDA) and other regulatory agencies regarding any DLTs or other AEs of interest.

For SAEs, the Investigator has to complete the SAE Form electronically in the electronic data capture (EDC) system for the study with as much information as possible and submit it in the time frame described in Section 8.6. When new significant information is obtained as well as when the outcome of an event is known, the Investigator should record the information in the EDC system. If the subject was hospitalized, a copy of the discharge summary and any other relevant hospital records (eg, admission report, laboratory test results, etc.) should be included as part of the subject's medical file.

All AEs in which the relationship is considered "yes" to study drug and all SAEs will be followed until resolved or until a stable status has been achieved. The type of follow-up (eg, phone, site visit, etc.) will be left to the discretion of the Investigator.

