5.5.5.4 Immune-related Hypothyroidism and Hyperthyroidism

Monitor thyroid function prior to and periodically (test for thyroid-stimulating hormone [TSH] and free thyroxine (FT4) every 4 to 6 weeks and as clinically indicated) during treatment with CX-072.

For Grade 1 hypothyroidism, CX-072 may be continued with close follow-up and monitoring of TSH and FT4. For Grade 2 hypothyroidism, CX-072 should be withheld, thyroid hormone supplementation prescribed for symptomatic subjects with any degree of TSH elevation or in asymptomatic subjects with TSH levels that persist >10 mIU/L (measured 4 weeks apart). Endocrinology consult should be considered. For Grade 3 hypothyroidism, CX-072 should be

held, supplementation prescribed, and endocrinology consult obtained. For Grade 4 hypothyroidism, treatment should be permanently discontinued, supplementation prescribed, and endocrinology consult obtained. May admit for IV therapy if signs of myxedema (bradycardia, hypothermia).

For Grade 1 hyperthyroidism, may continue CX-072 with close follow-up and monitoring of TSH and FT4 every 2 to 3 weeks until it is clear whether there will be persistent hyperthyroidism. For Grade 2 hyperthyroidism, CX-072 should be held, medical management initiated, and endocrinology consultation considered. For persistent hyperthyroidism (>6 weeks) or clinical suspicion, a workup for Graves' Disease should be initiated. For Grade 3 hyperthyroidism, CX-072 should be held, medical management initiated, and endocrinology consulted. For Grade 4 hyperthyroidism, treatment should be permanently discontinued, supplementation prescribed, and endocrinology consult obtained. For severe symptoms or concern for thyroid storm, should hospitalize subject and initiate prednisone 1 to 2 mg/kg per day or equivalent tapered over 1 to 2 weeks. May also use saturated solution of potassium iodide or thionamide (methimazole or propylthiouracil).

Consider that thyroiditis is transient and within weeks resolves to primary hypothyroidism or normal. Graves' disease is generally persistent and due to increased thyroid hormone production that can be treated with antithyroid medical therapy.

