8.5 Documentation of Adverse Events by Investigator

Subjects will be evaluated and questioned generally to identify AEs during the course of the study. Any events occurring prior to administration of the first dose, will be recorded on the Medical History eCRF. SAEs will be recorded on the Adverse Event eCRF from informed consent through 30 days following the last dose of CX-2009 and (for irAEs) through 90 days after administration of the last dose of CX-072. Events occurring after administration of the first dose of study drug will be recorded on the Adverse Event eCRF. AEs that occur up to and including 30 days after administration of the last dose of study drug must be reported in the EDC system.

All AEs spontaneously reported by the subject and/or in response to an open question from study personnel or revealed by observation, physical examination, or other diagnostic procedures will be recorded on the Adverse Event eCRF for that visit. Any clinically relevant deterioration in laboratory assessments or other clinical findings is considered an AE and must be recorded on the Adverse Event eCRF. In addition, an abnormal test finding will be classified as an AE if 1 or more of the following criteria are met:

- The test finding is accompanied by clinical symptoms;
- The test finding necessitates additional diagnostic evaluation(s) or medical/surgical intervention, including significant additional concomitant drug treatment or other therapy. Note: Simply repeating a test finding, in the absence of any of the other listed criteria does not constitute an AE;
- The test finding leads to a change in study drug dosing or discontinuation of subject participation in the clinical research study; and
- The test finding is considered clinically significant by the Investigator based on his/her medical judgment. If an abnormal laboratory result is recorded as an AE, then the corresponding laboratory value must be marked clinically significant in the database. Similarly, if an abnormal laboratory value is marked clinically significant in the database, there should be a corresponding AE entered.

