10.1.2.3. Thyroid Function

Blood for thyroid-stimulating hormone (TSH), Free T4 and T3 will be drawn in studies of Probody Tx that may induce an immune response.

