20. Serum pregnancy test (HCG) should be evaluated in all women of childbearing potential at Screening. If the Screening serum pregnancy test is obtained within 7 days of first infusion, the Day 1 pregnancy test may be omitted. Urine pregnancy test (with serum test as needed for confirmation) should be obtained prior to each study treatment infusion, at the EOT Visit, and at FU/EOS Visits through 50 days after the last dose of CX-2009 or 6 months after the last dose of CX-072, whichever is later.
21. Tumor marker assessments should be scheduled concurrently with CT for PSA and CA125 for appropriate tumor types; all others as clinically indicated.
22. For both Parts D1 and D2, on-treatment tumor biopsies will be optional. For the subjects who consent, tumor biopsies will be collected 3 to 5 days after the third dose of study treatment, provided that the tumor is accessible and a biopsy is deemed safe by the treating physician. Biopsy collection for the purpose of determining eligibility for Part D1 or D2 is not permitted.
23. Day 8 and Day 22 Visits are not needed for subjects who have been on study drug >4 months and have no ongoing \geq Grade 2 adverse events.
24. An EOT Visit will be conducted 30 days (± 7 days) after the last infusion of study treatment.
25. Follow-Up and EOS:
 - If subject had documented progression, the subject may continue in the study if experiencing clinical benefit (as assessed by the Investigator) following consultation with the Medical Monitor or designee; otherwise, the subject will continue in survival Follow-Up Visits every 3 months (± 14 days) after the EOT Visit for 1 year and then every 6 months (± 14 days) (this may be by telephone), or until death. Subsequent cancer treatment will be collected.
 - If subject has not had progression, imaging assessments will continue until progression is documented. Survival Follow-Up will be done every 3 months (± 14 days) as described above.
 - Women of childbearing potential will undergo pregnancy testing at FU/EOS Visits through 50 days after the last dose of CX-2009 or 6 months after the last dose of CX-072, whichever is later.

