- Cycle 1 Day 15: preinfusion
- Cycle 2 Day 1: preinfusion
- Cycle 2 Day 15: preinfusion (up to 1 day before infusion)
- Cycles 3, 4, 6, 8, and every 8 cycles thereafter: Day 1 preinfusion (up to 2 days before infusion)
- EOT (DOV)
- Follow-up Visit 1: Once any time >90 days after the last dose of CX-2009

ADA = antidrug antibody; DOV = day of visit; EOI = end of infusion; EOT = end of treatment; PK = pharmacokinetic.

Table 22. Schedule of PK and ADA Assessments: Part D1

Page 1 of 2

Period/Procedure	Cycle 1					Cycle 2					Cycles 3, 4, 6, 8 & Every 8 Cycles Thereafter	EOT	Follow-up Visit 1
	1	2	3	8	15	1	8	15	1				
Time of Draw	Preinfusion	Post-EOI	DOV	DOV	DOV	Preinfusion	Preinfusion	Post-EOI	DOV	Preinfusion	Preinfusion	DOV	DOV
CX-2009 Plasma PK ^a	X	X	X	X	X	X	X	X	X	X	X	X	X
CX-2009 Serum ADA ^b	X					X	X			X	X	X	X
CX-072 PK ^c	X	X				X	X	X		X	X	X	X
CX-072 ADA ^d	X					X	X			X	X	X	X

Notes: Part D1 cycle length is 28 days. Serial blood samples will be collected to characterize the PK of the CX-2009 and CX-072 and all drug-related moieties in all subjects. Blood samples will be collected to assess the extent of ADA response to the Probody therapeutic. Actual times of CX-2009 and CX-072 dosing and PK/ADA collection must be recorded.

^a CX-2009 PK samples will be drawn at the following times:

- Cycle 1 Day 1: preinfusion, 15 (±10) minutes post-EOI, and 1 hour (±10 minutes) post-EOI
- Cycle 1 Day 2 (±6 hours)
- Cycle 1 Day 3 (±12 hours)
- Cycle 1 Day 8 (±1 day)
- Cycle 1 Day 15 (±1 day)
- Cycle 2 Day 1: preinfusion, 15 (±10) minutes post-EOI, and 1 hour (±10 minutes) post-EOI
- Cycle 2 Day 8 (±2 days)
- Cycle 2 Day 15 (±1 days): preinfusion
- Cycles 3,4, 6, 8, and every 8 cycles thereafter: Day 1 preinfusion (up to 2 days before infusion)
- EOT (DOV)
- Follow-up Visit 1: Once any time >90 days after the last dose of CX-2009 or CX-072, whichever comes later

^b CX-2009 ADA samples will be drawn at the following times (to coincide with PK collections):

- Cycle 1 Day 1: preinfusion
- Cycle 1 Day 15: preinfusion
- Cycle 2 Day 1: preinfusion
- Cycle 2 Day 15: preinfusion
- Cycles 3, 4, 6, 8, and every 8 cycles thereafter: Day 1 preinfusion (up to 2 days before infusion)
- EOT (DOV)
- Follow-up Visit 1: Once any time >90 days after the last dose of CX-2009 or CX-072, whichever comes later

Table 22. Schedule of PK and ADA Assessments: Part D1

-
- ^c CX-072 PK samples will be drawn at the following times:

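### Parts D and E: the 90-day window for CX-072 immune-related AEs is not carried through the recording rule or the visit schedules, and the thyroid tests the Module requires are not scheduled

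*Protocol*

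**What the plan says.** **Recording window.** Section 8.4 defines the AE reporting period as 30 days after the last dose for AEs in general and "up to and including 90 days after administration of the last dose of study drug for all irAEs related to CX-072". It makes no distinction by seriousness. Section 8.5 reads differently. Its serious-event sentence, "SAEs will be recorded on the Adverse Event eCRF from informed consent through 30 days following the last dose of CX-2009 and (for irAEs", goes on to give irAEs 90 days after the last CX-072 dose. Its general sentence has no such extension: "AEs that occur up to and including 30 days after administration of the last dose of study drug must be reported in the EDC system". A third sentence in 8.5 has no end day: "Events occurring after administration of the first dose of study drug will be recorded on the Adverse Event eCRF".

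**Schedules.** In Tables 15 (Parts D1, D2) and 16 (Parts E1, E2) the AE row has its last entry at End of Treatment, and the cell under follow-up is empty. Footnote 3 of both tables ties AE review to infusions and to visits with a physical examination; none is scheduled after End of Treatment. The follow-up footnote says that after progression "the subject will continue in survival Follow-Up Visits every 3 months" (possibly by telephone). The PK and ADA schedules (Tables 22 to 25) set "Follow-up Visit 1: Once any time >90 days after the last dose of CX-2009 or CX-072, whichever comes later".

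**Thyroid.** Section 5.5.5.4 calls for thyroid monitoring before CX-072 and periodically during it: "test for thyroid-stimulating hormone [TSH] and free thyroxine (FT4) every 4 to 6 weeks and as clinically indicated". Core 10.1.2.3 says that TSH, "Free T4 and T3 will be drawn in studies of Probody Tx that may induce an immune response". Core 10.1.2 leaves the timing of laboratory tests to the Module's schedule. Tables 15 and 16 have no thyroid row, and their chemistry footnotes name no thyroid analyte.

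**The concern.** A site works mainly from the schedule of procedures and the recording rule. A site that follows Tables 15 and 16 and the general sentence of 8.5 would not systematically ask about, or be plainly required to enter, a non-serious CX-072 irAE with onset between Day 31 and Day 90. Yet 8.4 places that event inside the reporting period. Sites could resolve the conflict differently, so irAE counts would depend partly on which section a site had read.

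The thyroid point is similar. Several CX-072 actions in Table 10 and Section 5.5.5.4 depend on a TSH or FT4 result, including one for subjects without symptoms. If the test is missing from the schedule, whether that result exists depends on the site having read 5.5.5.4.

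The safety profile of the combination is a primary objective in Parts D1 and E1, and further safety characterisation is a secondary objective in D2 and E2.

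**Working it through.** No sample size or error rate is involved. The check is visit-day arithmetic plus a comparison of the rules.

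**Inputs**
- End of Treatment visit: 30 ±7 days after the last infusion, so Day 23 to 37 (Section 3.1.1; Tables 15 and 16).
- Next follow-up: 3 months after End of Treatment, ±14 days (same sources). I take 3 months as 90 to 92 days, nominally 91.
- irAE window: 90 days (8.4).
- Average treatment: about 6 months (3.1.1), taken as 26 weeks.
- Thyroid interval: 4 to 6 weeks (5.5.5.4).

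**Step 1. First all-subject visit after End of Treatment**
- Earliest: 23 + 90 − 14 = Day 99
- Nominal: 30 + 91 = Day 121
- Latest: 37 + 92 + 14 = Day 143

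All exceed Day 90, which agrees with the timing of Follow-up Visit 1 in Tables 22 to 25.

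**Step 2. Part of the 90-day window with no scheduled AE assessment**
- Nominal: 90 − 30 = 60 days; 60/90 = 67%
- End of Treatment at Day 37: 90 − 37 = 53 days; 53/90 = 59%
- End of Treatment at Day 23: 90 − 23 = 67 days; 67/90 = 74%

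**Step 3. Which rules capture a non-serious CX-072 irAE with onset at, say, Day 60?**
- 8.4 reporting period: yes.
- 8.5 serious-event sentence: no.
- 8.5 general EDC sentence: not required, because it is past Day 30.
- 8.5 open-ended sentence: yes, on its face.
- 8.7: yes, with 24-hour notice and no stated end day, if the event is on the list and meets the steroid or hormone-replacement definition.
- Section 5.6.1 and footnote 4 of Tables 15 and 16: the drug given for the irAE is recorded.
- Core 10.1.1: 30 days unless the Module says otherwise.
- AE row of Tables 15 and 16: no entry after End of Treatment.

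The same event is in or out depending on the sentence. A medication may be recorded without an AE that the general sentence requires to be entered.

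**Step 4. Thyroid tests**
- Implied on treatment: 26/6 = 4.3 to 26/4 = 6.5, so about 4 to 6, plus the test before CX-072.
- Scheduled in Tables 15 and 16: 0.

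**The case against.** The case on the other side has real content, and it rules out several stronger readings.

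- *There is no contact at all between Day 31 and Day 90.* A reader might infer this from the AE row, but it is wrong. Women of childbearing potential have monthly pregnancy tests through 6 months after CX-072, and subjects without progression continue imaging. These contacts carry no AE entry and do not reach every subject. The supportable statement is that there is no scheduled AE assessment.
- *Later visits are for survival only.* Section 3.1.1 also gives them the purpose of ensuring that toxicities resolve. That serves known events; it is not an instruction to look for new ones.
- *Recording of non-serious irAEs stops at Day 30.* The documents do not say so. The open-ended sentence in 8.5, the notification rule in 8.7 and the medication footnote all point beyond Day 30. SAP 12.1, written to an older Module amendment and for monotherapy, also describes AE collection through follow-up, but it only lists events from Day 31 onwards and leaves them out of the summaries. What stands is a contradiction.
- *Two thirds of late irAEs would be lost.* The 67% is a share of time, not of events. AEs can be collected retrospectively, and a question at Follow-up Visit 1 would do that. The defect is that no such question is scheduled.
- *Thyroid tests would not be done, and hold rules could not operate.* Section 5.5.5.4 is itself binding Module text, and the Table 10 recovery rule accepts Grade 1 or lower as an alternative to baseline. What stands is that the schedule omits tests the text requires.
- *Section 5.5.5.8 requires ACTH and cortisol in everyone at Screening.* Its mention of baseline can equally be read as the start of a diagnostic work-up.
- *Dose-finding would be distorted by late irAEs.* D1 and E1 decisions use DLTs over 28 and 21 days and delayed AEs over 6 weeks. Events 31 to 90 days after the last dose would not normally enter them.

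**Conclusion.** The point holds as an internal contradiction in the Module for Parts D and E. Section 8.4 sets one window for all CX-072 irAEs; 8.5 applies it explicitly to serious events only; and the schedules place no AE assessment in, or looking back on, about 60 of its 90 days (53 to 67). Required thyroid testing amounts to about 4 to 6 on-treatment tests plus one beforehand, against none scheduled.

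These figures assume 3 months is 90 to 92 days, that visits fall within their stated windows, and that average treatment is about 26 weeks. The conclusion that the next all-subject visit falls after Day 90 does not depend on the exact values, since Tables 22 to 25 say so directly.

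A reader might infer that irAEs were under-counted in this trial. The documents do not support that. The SAP (4.2 and Section 8) accounts for all 99 treated subjects in Parts A, A2, B and C1, states that none entered D1 or D2, and does not include Part E. The consequence is for the protocol text, and would become practical if a combination part opened or the text were reused.

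**What to change.** - Reconcile 8.5 with 8.4, 8.7 and the concomitant-medication footnote so that one stated recording window applies to all CX-072 irAEs, serious or not.
- Add an AE entry to the follow-up column of Tables 15 and 16, so that Follow-up Visit 1, when blood is already drawn, captures irAEs with onset inside that window.
- Reconcile Tables 15 and 16 with the thyroid testing already stated in 5.5.5.4 and Core 10.1.2.3, using visits and blood draws already scheduled. This asks for consistency with the Module's own text and proposes no new monitoring rule.
- Clarify whether baseline in 5.5.5.8 means Screening or the start of a work-up.

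The cost is a wording and schedule amendment, some additional AE entries, and thyroid assays that the Module already calls for. No new visit is needed. If 5.5.5.8 is clarified to mean Screening, its morning ACTH and cortisol samples would be an added cost.
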